The here proposed study, conducted in patients undergoing surgery, aims to 1) describe the incidence and types of postoperative pulmonary complications (PPCs), 2) describe patient demographics, baseline characteristics, and intraoperative ventilation management, 3) describe the occurrence of intraoperative adverse events (IAEs), and 4) their associations with PPCs, and 5) assess the practice of intraoperative mechanical ventilation.

Study design

This is an observational investigator–initiated, international, multicenter, prospective, cross–sectional study.

Local investigators will capture data in an electronic CRF (eCRF), including patient demographics and baseline characteristics, intraoperative ventilator settings and ventilation parameters, and outcomes.

Study population

Patients are eligible for participation if: 1) adult and 2) receiving intraoperative ventilation during general anesthesia for surgery. We will exclude patients receiving ventilation outside of an operating room as well as patients receiving intraoperative ventilation during extracorporeal life support.

Main study endpoints

The primary endpoint is to report the number of patients with PPCs occurring in the first 5 postoperative days. As secondary endpoint, the practice of mechanical ventilation in patients undergoing general anesthesia for surgery will be ascertained including key intraoperative ventilator characteristics and respiratory system mechanics. Other secondary endpoints will include: incidence and type of IAEs; postoperative complications other than PPCs in the first 5 postoperative days; impact of intraoperative hemodynamic management on the occurrence of

PPCs, intensive care unit (ICU) admission and length of stay, hospital length of stay, and hospital mortality on day 28.

Study duration

The overall duration of the study is 18 months, with 9 months allocated for enrollment and data collection, and 9 months dedicated to statistical analysis.

Participating hospitals have to prospectively collect data in a consecutive manner within a predefined period of 1 week (7 days). Also, participating hospitals can decide on which period they choose to collect data, but data collection must take place during a predetermined time window of 8 weeks, following the ethical committee/internal review board approval.

Nature and extent of the burden and risks associated with participation, benefit and group relatedness

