Weaning phase: at beginning and at the end of weaning phase, the following variables will be acquired: ventilatory mode, Vt (ml), PEEP (cmH₂O), pressure support over PEEP (if any) (cmH₂O), inspiratory trigger regulations, FiO₂, respiratory rate (breaths/min), SpO₂ (%), EtCO₂(mmHg or kPa), mean, systolic, and diastolic arterial pressure (either invasive or non-invasive), mmHg, heart rate (beats per minute).

It will also be recorded if aspiration is performed prior to tube removal. The number and type of IAEs will be acquired throughout the whole duration of surgical and anesthesiologic procedures (see "11" for definitions).

Peri-operative variables: duration of anesthesia procedure, duration of surgical procedure, tube type and size, type of anesthesia, type of analgesia (total endovenous, antibiotic prophylaxis, details on neuromuscular function monitoring and about the use of reversal agents (if any), total intra-operative fluid and total transfusion of blood products, temperature and hemoglobin at end of surgery (if clinically available). The possible admission to post-anesthesia care unit (PACU) and the eventual administration of non-invasive respiratory support (NIRS), namely, high flow oxygen therapy, continuous positive airway pressure, and non-invasive bilevel positive airway pressure ventilation, and the settings will be recorded.

Post-operative variables: vital signs involving SpO₂, heart rate, systolic, diastolic, and mean arterial pressure, body temperature if assessed, eventual arrythmias occurrence, and the blood gas analysis parameters (optional assessment) will be hourly collected in the immediate post-operative period or PACU stay, and at the discharge to surgical ward or ICU.

Follow up (day 0 to 5): PPCs are recorded from the medical chart on day 0 (end of surgery to 23:59h) and on days 1,2,3,4 and 5 post-operative (each day runs from 00:00 AM to 23:59 PM). Follow–up is completed on the day of discharge or on day 5 if the patient is still admitted.

On day 0 the following variables are collected: IMV after discharge from the operation room, admission to ICU/PACU after surgery, PPCs (see "11").

On day 1,2,3,4 and 5 the following variables will be collected: any new admission to ICU; any new or prolonged IMV; PPCs (see "11").

The data mentioned above are considered essential to defined as "complete" each patient's medical record.

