11. DEFINITIONS

11.1. PPCs definition

For PPCs (within a time window ranging from day of surgery to 5 days after surgery) we intend unplanned supplementary oxygen administration for hypoxemia, i.e., as oxygen saturation less than 90% in room air, but excluding oxygen supplementation given as standard care, e.g. directly after arrival in the post-anesthesia care unit, respiratory failure defined as oxygen saturation less than 90% despite oxygen therapy or need for non-invasive respiratory support (NIRS), unplanned new or prolonged IMV (after discharge from the operating room), acute respiratory distress syndrome (ARDS) (25), pneumonia (presence of a new or progressive radiographic infiltrate and at least two of three clinical features; fever >38°C, leucocytosis, or leukopenia (white blood cells count >12000 cells*µl-3 or <4000 cells*µl-3 and purulent secretions), pneumothorax, pneumomediastinum, and atelectasis (all confirmed through chest radiograph, computed tomography and/or thoracic ultrasonography).For NIRS we intend high flow oxygen therapy, continuous positive airway pressure, and non-invasive bilevel positive airway pressure ventilation.

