11.2. IAEs definition

IAEs include episodes of hypoxia (SpO2<92%), use of unplanned lung recruitment maneuvers (ventilation strategies aimed to restore aeration of the lungs); airway pressure reduction (ventilation strategies aimed to lower peak and plateau pressure), presence of expiratory flow limitation (expiratory flow higher than zero at end-expiration as suggested by visual analysis of the expiratory gas flow curve), use of vasoactive drugs (any given to correct hypotension), and new arrhythmias (atrial fibrillation, sustained ventricular tachycardia, supraventricular tachycardia, or ventricular fibrillation).

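### The recording windows for intraoperative adverse events and pulmonary complications overlap at emergence, so one desaturation can be coded as both a hypoxia IAE and a respiratory-failure PPC

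*Protocol*

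**What the plan says.** **Exposure window.** Protocol 5.2 (weaning phase): "The number and type of IAEs will be acquired throughout the whole duration of surgical and anesthesiologic procedures". IAE capture therefore ends when anesthesia ends.

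**Outcome window.** Protocol 5.2 (follow-up, day 0 to 5): "PPCs are recorded from the medical chart on day 0 (end of surgery to 23:59h". Section 11.1 is no more precise and places PPCs "within a time window ranging from day of surgery to 5 days after surgery".

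**Two different end times.** Section 5.2 records "duration of anesthesia procedure, duration of surgical procedure" as separate items, so the protocol itself distinguishes the end of surgery from the end of anesthesia.

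**Content of the events.** Section 11.2: "IAEs include episodes of hypoxia (SpO2<92" (per cent), with no condition on inspired oxygen. Section 11.1 counts as a PPC "respiratory failure defined as oxygen saturation less than 90% despite oxygen therapy or need for non-invasive respiratory support (NIRS", with no minimum duration and no limit on place. Within 11.1, only new or prolonged invasive ventilation is tied to having left the operating room. The exclusion of oxygen given as standard care is attached to the supplementary-oxygen component.

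**Use.** The main objectives in the Summary are, among others, to "describe the occurrence of intraoperative adverse events (IAEs), and 4) their associations with PPCs".

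**The concern.** An exposure should be complete before the outcome can begin. Here weaning, extubation and emergence fall after the end of surgery but before the end of anesthesia, so they belong to both windows. A patient whose saturation falls to 88% on oxygen at extubation in the operating room satisfies the hypoxia IAE and the respiratory-failure PPC with a single event, and nothing in the protocol assigns that event to one side.

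Two results are at stake. The association between IAEs and PPCs would be partly an association of an event with itself. Confounder adjustment as described in section 6 would not remove that, because it is not confounding. The primary PPC count would also include some desaturations that occurred before the patient left the operating room.

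**Working it through.** **1. Do the windows overlap?** IAE capture runs from the start of the procedure to the end of anesthesia. PPC capture runs from the end of surgery to day 5 or discharge. The interval from end of surgery to end of anesthesia is in both.

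**2. Which events in that interval meet both definitions?**

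| Event between end of surgery and end of anesthesia | IAE (11.2) | PPC (11.1) |
|---|---|---|
| SpO2 below 90% on oxygen | yes, hypoxia | yes, respiratory failure |
| SpO2 below 92% with need for non-invasive support | yes, hypoxia | yes, respiratory failure |
| SpO2 from 90% to below 92% on oxygen, no such support | yes, hypoxia | no |
| New or prolonged invasive ventilation | not listed | only after operating-room discharge |
| Vasoactive drug, new arrhythmia, expiratory flow limitation | yes | no |

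The room-air oxygen component of the PPC composite will seldom apply while the patient is still on oxygen. The overlap is real but is essentially confined to hypoxia.

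**3. The plan's own figure.** Section 4.4 gives a confidence interval width of 0.0119 for a 10% rate in 10,000 patients (Clopper-Pearson). With 1,000 events in 10,000 the exact 95% limits are 0.0942 and 0.1060, width 0.01186. The figure reproduces, and this point does not affect it. The half-width is 0.0119 / 2 = 0.00595, about 0.6 percentage points.

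**4. Bias in the odds ratio (OR) if there is no true association.** Let o be the share of all patients with one double-coded event. Among the others, let q be the IAE prevalence and p the PPC rate, independent of each other. The cell probabilities are:

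- IAE and PPC: a = o + (1 − o)qp
- IAE only: b = (1 − o)q(1 − p)
- PPC only: c = (1 − o)(1 − q)p
- neither: d = (1 − o)(1 − q)(1 − p)

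Then OR = ad / (bc) = 1 + o / [(1 − o)qp].

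Only p = 0.10 comes from the protocol (4.4). The values of o and q are assumptions. Example: o = 0.01, q = 0.30 gives 1 + 0.01 / (0.99 × 0.03) = 1.34.

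| Double-coded share o | OR, q = 50% | OR, q = 30% | OR, q = 5% | Rise in PPC rate, o(1 − p) |
|---|---|---|---|---|
| 0.1% | 1.02 | 1.03 | 1.20 | 0.09 points |
| 0.5% | 1.10 | 1.17 | 2.01 | 0.45 points |
| 1% | 1.20 | 1.34 | 3.02 | 0.9 points |
| 2% | 1.41 | 1.68 | 5.08 | 1.8 points |

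The columns for 50% and 30% stand for any IAE; the column for 5% stands for a single, rarer IAE such as hypoxia.

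**5. Would it show at this sample size?** With 10,000 patients and Woolf 95% intervals at q = 30%, the spurious OR is 1.03 (0.90 to 1.19) at o = 0.1%, 1.17 (1.02 to 1.34) at 0.5% and 1.68 (1.48 to 1.90) at 2%. At q = 5% it is 1.20 (0.91 to 1.58) at o = 0.1% and 2.01 (1.60 to 2.52) at 0.5%.

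**6. How extreme is the largest figure?** At q = 5% and o = 2%, total hypoxia prevalence is 0.02 + 0.98 × 0.05 = 0.069. Double-coded emergence events would then be 0.02 / 0.069 = 29% of all hypoxia IAEs.

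**The case against.** **The association is not central to the body of the protocol.** It is named in the Summary only. Section 2.2 lists the occurrence of IAEs, 5.1.2 their incidence and type, and the regression in section 6 concerns patient characteristics. This stands. A reader might infer that a specified main analysis is invalid; the protocol specifies no such model. An objective stated in the Summary still has to be answerable from the data as captured.

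**Sites may not code it twice.** Day-0 PPCs are taken from the chart, next to items that clearly follow the operating room, and a site may well not record a momentary dip at extubation as respiratory failure. This also stands: double coding is possible, not certain. But a site that follows the stated day-0 start will include emergence.

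**Brief dips count anyway.** Section 11.1 sets no minimum duration, so a short desaturation in the recovery unit is a PPC too. That weakens the argument about the primary count, since disjoint windows change only where counting begins. It does not touch the argument about the association.

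**The analysis plan could deal with it.** A sensitivity analysis dropping PPCs before operating-room exit could be planned there. However, the day 0 to 5 follow-up records PPCs by calendar day, so the data may not allow double-coded events to be separated later. The rule belongs at data capture.

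**Conclusion.** As written, the two windows overlap during emergence and one hypoxic event can be both exposure and outcome. That much follows from the text alone. The consequence is a possible upward bias in the IAE-PPC association, mainly for the hypoxia IAE, and a possible small increase in the primary PPC count.

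The size cannot be determined from the documents, which give neither the IAE prevalence nor the share of patients affected. Over assumed shares of 0.1% to 2%, the range runs from negligible (OR 1.03 at 30% IAE prevalence) to large (5.1 at 5%), and the top of that range is an extreme case. The rise in the PPC rate stays below the planned half-width of about 0.6 points unless the share exceeds roughly 0.00595 / 0.9 = 0.66%.

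A reader might conclude that IAEs in general are contaminated, or that any reported IAE-PPC association would be an artefact. The documents do not support this: the other IAE types share little or no content with a PPC, the ventilation component is already separated, and a share near 0.1% would hardly be visible for any IAE taken together. The point deserves a clarification before data capture; it does not invalidate the registry.

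**What to change.** Make the windows disjoint at one time point, operating-room discharge, which 11.1 already uses for invasive ventilation:

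- **5.2 and 11.1:** start day 0 at operating-room discharge for every PPC component, and state that a PPC requires its criterion to be met after that time.
- **5.2 and 11.2:** end IAE capture at the same time, so that an event confined to the operating room is an IAE only.
- **eCRF:** repeat the rule in the help text.

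A desaturation that begins in the operating room and still meets a PPC criterion afterwards would count on both sides. That is acceptable, because the outcome is then observed after the exposure window has closed. Ending IAE capture at the end of surgery, or starting PPCs at the end of anesthesia, would also separate the windows; operating-room discharge has the advantage of being in the definitions already.

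The cost is short edits in three sections and a help text, with no additional data. The downside is that a few emergence events move from the PPC count to the IAE count.

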5. METHODS

5.1. Study Outcome

5.1.1. Primary outcome

The primary endpoint is to report the number of patients with PPCs, considered as a composite incidence of predefined postoperative pulmonary complications occurring in the first 5 postoperative days or hospital discharge whichever comes first, examining also individual PPCs incidence and type (for the definitions of PPCs see '11').

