ICU or PACU admission: recording of data during the critical care submission can be left out by the participating centers if this workload exceeds their possibilities. However, it is requested to collect the ICU/PACU data. In case of IMV and/or admission to the ICU/PACU during the follow-up period (day 0, 1, 2, 3, 4 or 5), the following variables will be collected on a different CRF: reason for ICU/PACU admission, reason for IMV or NIRS, APACHE II score (24), on (first) admission to and within the first 24 hours in ICU (i.e., the APACHE II score to be collected and reported for patients who were in the ICU before surgery, and were referred to the ICU after surgery, starts direct after the first admission to the ICU; the APACHE II score to be collected and reported for patients who were not in the ICU before surgery, but were referred to the ICU after surgery, starts direct after surgery, in the ICU). At the first hour of ICU/PACU admission and in case of continued admission each day (during morning rounds) the following variables are collected: SOFA score, IMV regulations, arterial blood gas values (pH, PaCO₂, PaO₂ if available), closest to 08:00 AM, PPCs (number and type, see "p 11"), extra-pulmonary organ failure (number and type), and risk factors for respiratory failure (number and type).

If a patient is transferred back to the ward, the non–ICU/PACU follow–up CRF will be used to record the variables of the remaining follow–up days.

Follow up (day 28): On day 28 ICU and hospital length of stay as well as in hospital death are assessed.

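### Protocol section 5.2 contradicts itself on whether PPCs must be recorded on ICU/PACU days, so a permitted omission could remove primary-endpoint data

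*Protocol*

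**What the plan says.** Section 5.1.1 defines the endpoint: "The primary endpoint is to report the number of patients with PPCs, considered as a composite incidence of predefined postoperative pulmonary complications", counted over the first five postoperative days or until discharge if earlier.

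Two paragraphs of section 5.2 govern how it is collected.

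- **Follow up (day 0 to 5).** "PPCs are recorded from the medical chart on day 0 (end of surgery to 23:59h") and then on each of days 1 to 5 until discharge. ICU/PACU patients are not excluded. The day 0 items include ventilation after leaving the operating room and ICU/PACU admission. The items for days 1 to 5 include new ICU admission and new or prolonged ventilation. PPCs are listed beside them each time. The closing sentence makes all data listed up to that point essential for a complete record.
- **ICU or PACU admission.** It opens with the waiver, "recording of data during the critical care submission can be left out by the participating centers if this workload exceeds their possibilities", followed by "However, it is requested to collect the ICU/PACU data". A separate form applies to ventilated patients and to those with "admission to the ICU/PACU during the follow-up period (day 0, 1, 2, 3, 4 or 5"). The instruction for these patients is that "the following variables will be collected on a different CRF". The items for the first hour and for each further day include "PPCs (number and type, see 'p 11'), extra-pulmonary organ failure (number and type), and risk factors for respiratory failure (number and type"). After return to the ward, the non-ICU/PACU "CRF will be used to record the variables of the remaining" follow-up days.

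**The concern.** The waiver covers data recorded during the critical-care stay without limit, and the form it covers carries the primary endpoint. The sentence on return to the ward suggests that the ward form is not in use during the stay. A centre could therefore follow the ICU/PACU paragraph as written and record no PPC entry for those days.

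Such a loss would not be random. Ventilation after surgery triggers the separate form, and unplanned new or prolonged ventilation is itself a PPC component (section 11.1). Use of the waiver depends on workload, in a voluntary registry without financial incentive (section 3.1). The overall incidence could be biased downward. The planned comparisons by cardiac surgery, urgency and geo-economic setting (section 6) could be distorted if ICU use or omission differs between the groups. Each centre collects for one week only, so a rule misread at the start is hard to correct later.

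**Working it through.** **1. The plan's own precision figure.** Section 4.4 gives a 10% rate, 10,000 patients and the Clopper-Pearson method; Figure 1 gives the 95% level. With x = 1,000 and n = 10,000:

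- lower limit = 0.025 quantile of Beta(1000, 9001) = 0.09419
- upper limit = 0.975 quantile of Beta(1001, 9000) = 0.10605
- width = 0.01186, which rounds to the stated 0.0119; half-width = 0.0059, or about 0.6 percentage points

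The figure is reproduced and is not in dispute. It serves as the yardstick below.

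**2. The two paragraphs applied to a patient in ICU on days 1 to 3 and on the ward on days 4 and 5, at a centre that uses the waiver.**

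| Item | Follow-up paragraph governs | ICU/PACU paragraph governs |
|---|---|---|
| PPC entry, days 1 to 3 | required | may be left out |
| New ICU admission, new or prolonged ventilation | required | listed as core items, so still expected |
| Reason for ventilation or non-invasive support | separate form only | may be left out |
| PPC entry, days 4 and 5 | required | required (ward form resumes) |

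The core ventilation item does not replace the PPC entry. Section 11.1 counts ventilation only if it is unplanned, and the reason for ventilation sits on the form that may be skipped. Pneumonia, ARDS, atelectasis and respiratory failure cannot be derived from admission and ventilation flags.

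**3. Illustration of size.** Only the 10% overall rate comes from the protocol. The other inputs are assumptions:

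- f = share of patients in ICU = 10%
- r = PPC risk among them = 30%
- q = fraction of them whose form is omitted = 20% or 50%
- every PPC in an omitted patient is lost

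If lost PPCs are counted as none, observed rate = 0.10 − f·q·r. If omitted patients are excluded, observed rate = (0.10 − f·q·r) / (1 − f·q).

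| q | f·q·r | Counted as none | Fall | Excluded | Fall |
|---|---|---|---|---|---|
| 20% | 0.006 | 9.40% | 0.60 points | 0.094/0.98 = 9.59% | 0.41 points |
| 50% | 0.015 | 8.50% | 1.50 points | 0.085/0.95 = 8.95% | 1.05 points |

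**4. Range.** With f from 5% to 20%, r from 20% to 40% and q from 10% to 50%, the fall is 0.1 to 4.0 points (counted as none) or 0.05 to 3.3 points (excluded).

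**5. Partial capture.** Let c be the share of these patients' PPCs recorded elsewhere, on ward days or through the core items. The counted-as-none fall becomes f·q·r·(1 − c). With f = 10%, r = 30% and c = 50%, it is 0.30 points at q = 20% and 0.75 points at q = 50%. With c = 100%, which is the result if the follow-up paragraph is applied on ICU/PACU days, it is zero. The fall reaches the 0.59-point half-width at q = 0.0059/0.030, about 20%, when c = 0, and at q = 0.0059/0.015, about 39%, when c = 50%.

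**The case against.** The strongest answer is that the follow-up paragraph already settles the matter. It covers all patients, was plainly written with ICU/PACU patients in view, and makes day 0 to 5 PPCs essential. On that reading, the separate form is an add-on that merely repeats PPCs, and a record without PPCs on an ICU day is incomplete. Much of this stands. A reader might infer from the waiver that the primary endpoint is simply optional in critical-care patients; the protocol does not support that. It shows two instructions that disagree. But it never says that the follow-up paragraph prevails, and the paragraph granting the omission is the later and more specific one.

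Several further points also stand in part:

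- **PACU.** A reader might infer that day 0 PPCs of routine PACU patients are generally optional. The core items list PACU admission and PPCs together on day 0, and PACU observations and non-invasive support are recorded before the essential-data sentence. PACU admission alone also need not mean high risk.
- **Surviving data.** The endpoint is per patient, so one PPC on any recorded ward day is enough, and the core ventilation item would still be captured. Step 3 is therefore an upper-end case for its inputs.
- **Missing data.** Section 6 foresees multiple imputation or complete-case analysis, plus sensitivity analyses. Imputation using ICU admission and ventilation status might recover part of the loss. It cannot reliably repair omission that depends on the outcome itself, and complete-case analysis gives the excluded column above.
- **Figure 2.** It may show which form runs when, but it is not visible in the text available here.

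**Conclusion.** The point holds as an unresolved conflict within section 5.2. If centres use the waiver as worded, primary-endpoint data can go missing in relation to outcome and workload.

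The size is unknown, because the protocol gives no ICU share, no PPC risk by location and no expected omission rate. On the illustrative inputs the fall is about 0.4 to 1.5 points on a 10% rate. It is near zero if PPCs are recorded on ICU/PACU days regardless. In the excluded case, a downward bias also requires that the omitted patients have a PPC risk above the overall rate. This is plausible, because ventilation triggers the form, but the protocol does not show it. Bias in the planned comparisons is likewise a possibility, not a demonstrated result.

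The conflict still deserves correction. The registry is sized solely for precision, moderate omission could exceed the planned margin, and neither more patients nor an analysis plan can restore outcomes that were never recorded.

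**What to change.** Amend the ICU/PACU paragraph of section 5.2 to say three things:

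- Daily PPCs, together with the ventilation and ICU/PACU admission items of the follow-up paragraph, are mandatory on every in-hospital day from 0 to 5, wherever the patient is.
- These items are entered on the core follow-up form, which continues during an ICU/PACU stay.
- The workload waiver covers only the additional critical-care variables, such as APACHE II, SOFA, ventilator settings and blood gases.

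Set the core items as required fields in the eCRF, so that an empty PPC entry cannot pass as the absence of a PPC. As a secondary clarification, state whether the day 28 fields belong to a complete record. They come after the sentence that defines it, although the waiver itself does not mention them.

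The cost is a one-paragraph amendment, required-field flags, and a little extra chart review at centres that would have used the waiver. The sample size is unaffected.
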